#### **17.3.5.3 Safety Analyses**

An AE will be considered a treatment-emergent adverse event (TEAE) if

1. AE that was not present before the first dose in the MT-1186-A01 study but starts after administration of the first dose of study drug in the current study, or
2. AE that started after the first dose in the MT-1186-A01 and is ongoing in the current study, or
3. AE that was present before the first dose in the MT-1186-A01 study but increased in severity following administration of the first dose of study drug in the current study.

TEAEs will be coded using the latest available version of the MedDRA and will be summarized in incidence tables by SOC and PT. The numbers and proportions of subjects with TEAEs will be calculated by SOC and PT. The following summaries will be presented:

- TEAEs by SOC and PT
- TEAEs by SOC, PT, and severity
- TEAEs by SOC, PT, and drug relationship

- TEAEs leading to discontinuation of study drug by SOC and PT
- TEAEs leading to death by SOC and PT
- TEAEs related to study drug by SOC and PT
- TEAEs related to study drug by SOC, PT, and severity
- Serious TEAEs by SOC and PT
- Serious TEAEs related to study drug by SOC and PT

For each of the summaries, multiple occurrences of the same event within a subject will be counted once in the summaries by SOC and PT; multiple occurrences of the same event within a subject will be counted once in the maximum severity category (severe > moderate > mild) and/or maximum study drug relationship category (reasonable possibility/no reasonable possibility). If severity or relationship is found to be missing the most severe occurrence will be imputed for that particular summary.

All AEs for each subject, including multiple occurrences of the same event, will be presented in a full comprehensive listing including subject number, severity, seriousness, action taken, outcome, relationship to treatment, onset/stop date and duration.

Duration of the AE and time to the AE occurrence from start of oral edaravone will be calculated and presented in days (duration = AE stop date – AE start date + 1 and time to AE occurrence = AE start date – The first administration date of study drug + 1).

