8.4.1.3. Concomitant Medication

Definition of concomitant medications:

At Day 1³, subjects will be asked what medications (including riluzole) they are taking and the information will be recorded in the subject's source documents and eCRF.

Concomitant medication is defined as any medication, other than the study drug, which is taken from first dose date in the MT-1186-A03 study up to week 96 Visit, including prescription, herbal and over-the-counter medications. All concomitant medications taken while the subject is participating in the study will be recorded in the eCRF.

All medications will be classified using the Anatomical Therapeutic Chemical (ATC) classification codes and preferred drug names from the World Health Organization Drug Dictionary (WHO-DD, version from September 2019).

Rules to determine concomitant medications during MT-1186-A03

Medications with start date or stop date on or after the first dose date in the MT-1186-A03 study or ongoing at study week 96 visit will be considered concomitant medications.

If the medication start date is incomplete, then it will be imputed as follows for the purpose of determining concomitant use:

- If the start date is completely missing, the start date will be equal to the date of first dose in the current study. However, if the stop date is not missing and is before the first dose date, then the stop date will be used instead.
- If the start day is missing, the first day of the month will be used.

³ Based upon Week 48 procedures from MT-1186-A01

- If the start day and month are missing, then the first day of the first month (January) will be used.

If the medication stop date is partial, then it will be imputed as follows for the purpose of determining concomitant use:

- If the stop date is completely missing and the medication is not ongoing, the stop date will be equal to the last study drug dose date or date of completion /withdrawal, whichever is the latest.
- If the stop day is missing, the last day of the month will be used.
- If the stop day and month are missing, then the last day of the last month (December) will be used.

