8.4.3.1. Adverse Events

An AE is any untoward medical occurrence in a subject or clinical investigation subject administered a pharmaceutical product that does not necessarily have a causal relationship with this IMP. An AE can therefore be any unfavorable and unintended sign (including an abnormal laboratory finding, for example), symptom, or disease temporally associated with the use of an IMP, whether or not considered related to the IMP.

Adverse events will be coded according to the MedDRA version 23.0.

AEs will be classified for Treatment Emergent AEs (TEAEs) if at least one of the following conditions is met:

- AE that was not present before the first dose in the MT-1186-A01 study but newly starts after administration of the first dose of study drug in the current study, or,
- AE that was present before the first dose in the MT-1186-A01 study but increased in severity following administration of the first dose of study drug in the current study.

- **Handling Partial Dates:**

Events with a missing start time, but with a start date equal to the date of first dose of study treatment in the current study will be considered treatment-emergent.

If the AE start date is incomplete, it will be imputed as follows for the purpose of determining TEAE, AE duration and AE Onset Cycle:

- If the start date is completely missing, the start date will be equal to the date of the first dose date of study treatment in the current study. However, if the stop date is not missing and is before the date of the first dose of study treatment, then the stop date will be used instead and the AE will not be considered as TEAE.
- If the start day is missing, but the month and year are not missing and are equal to the month and year of the first study dose in the current study, then

this event will be considered as TEAE.

- If the start day and month are missing, then the first day of the first month (January) will be used.

If an AE stop date is incomplete, it will be imputed as follows for the purpose of determining AE duration:

- If the AE stop date is completely missing, then the stop date will be equal to the subject's last observed date.
- If the Stop day is missing, but the month and year are not missing and are equal to the month and year of the last observed date, then stop date will be equal to last observed date.
- If the start day and month are missing, then the first day of the first month (January) will be used.

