AEs will be classified for ADR if an AE is evaluated as having causally related to the investigational product with “a reasonable possibility”

Serious Adverse Events

A SAE is defined as any untoward medical occurrence that at any dose:

- Results in death;
- Is life-threatening;
- Requires hospitalization or prolongation of existing hospitalization;
- Results in persistent or significant disability or incapacity;
- Is a congenital anomaly or birth defect;
- Is an important medical event;

All SAEs occurring from the time written ICF is obtained from a subject until the end of the Safety Follow-up period or the withdrawal of the subject from the study must be reported to the Sponsor/CRO. All SAEs must also be entered in the AE section of the eCRF within 24 hours.

Duration of Adverse Events

Duration of the AE and time to the AE occurrence from Day 1 will be calculated and presented in days

Duration = AE stop date – AE start date + 1

Time to AE occurrence = AE start date – Day1 + 1.

Definition of Oral subgroup and PEG subgroup

The patients start with oral administration or PEG administration. The former can switch from oral administration to PEG/RIG dosing based the patient's disease progresses. Therefore, if the subject started with PEG/RIG or switched from oral dosing to receiving study medication through PEG/RIG during MT-1186-A01 or MT-1186-A03, then the subjects will be classified to PEG subgroup. Otherwise, the subjects will be classified as Oral subgroup.

If a switch date is incomplete and the switch day is missing, then the 15th day will be used.

Definition of TEAE under Oral dosing and PEG dosing

If the subjects have the date subject switched to PEG/RIG dosing during MT-1186-A01 or MT-1186-A03, TEAEs after the switched date will be defined as TEAEs under PEG dosing. Otherwise TEAEs will be defined as TEAEs under Oral dosing.

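### The AE stop-date list in the SAP ends with a copy of the start-date bullet, so stop dates known only by year have no valid rule for AE duration

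*SAP*

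**What the plan says.** SAP 8.4.3.1, under the handling of partial dates, introduces the second of its two lists with "If an AE stop date is incomplete, it will be imputed as follows for the purpose of determining AE duration". The list has three bullets:

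- Stop date wholly missing: "If the AE stop date is completely missing, then the stop date will be equal to the subject's last observed date".
- Day missing, month and year known: a rule is given only where these are "equal to the month and year of the last observed date, then stop date will be equal to last observed date".
- Third bullet: "If the start day and month are missing, then the first day of the first month (January) will be used". The same sentence closes the start-date list just above it.

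The same section then states that "Duration of the AE and time to the AE occurrence from Day 1 will be calculated and presented in days", with the formula "Duration = AE stop date – AE start date + 1". Protocol section 17.3.5.3 gives the same formula and requires a full AE listing that includes "relationship to treatment, onset/stop date and duration".

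For concomitant medications, SAP 8.4.1.3 handles the parallel case differently: "If the stop day and month are missing, then the last day of the last month (December) will be used". It uses the last day of the month when only the day is missing.

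**The concern.** The third bullet speaks of a start date inside a list about stop dates, and assigns the earliest day of the year. An end date should not be pushed to the earliest possible value, because that can place it before the onset. The bullet also runs against the first bullet of its own list, where a stop date with no information at all goes to the last observed date. A site that supplies the year would therefore get a shorter, and often impossible, duration than a site that supplies nothing.

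What is at stake is the AE duration that both documents say will be calculated and presented. Negative values would be noticed and queried. Positive but shortened values, from onsets in an earlier year, could pass unnoticed.

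**Working it through.** The documents state no figure on this point, so there is none to reproduce. The check is date arithmetic with the SAP's own formula. The calendar dates below are illustrative and do not come from the documents.

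**Inputs.** Duration = stop - start + 1 (SAP 8.4.3.1). Year-only stop set to 1 January (third bullet, applied to stop dates). Neither document sets a floor at the start date.

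**Onset and stop in the same 365-day year.** Let the onset be day k of the year. The imputed stop is day 1, so duration = 1 - k + 1 = 2 - k.

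- k = 1 gives 1 day; k = 2 gives 0.
- k = 3 to 365 gives -1 to -363. That is 363 of the 365 possible onset dates.
- Onset 15 June 2022 is day 166: 2 - 166 = -164 days.

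**Size of the error.** If the true stop is day m of its year, imputed minus true duration = 1 - m, whatever the onset date. This runs from 0 (m = 1) to -364 (m = 365), so the rule never overstates.

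- Onset in an earlier year: the duration stays positive but is 0 to 364 days short, on average 182 if the true stop is uniform over the year (mean m = 183).
- Onset in the same year: averaged over all valid onset and stop pairs, the error is about -243 days.
- Onset and stop both known only by the same year: both become 1 January, and the duration is always 1 day.

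**Literal reading.** If the bullet governs start dates, as its words say, no bullet covers a year-only stop date and the duration cannot be derived.

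**Day-only gap.** The second bullet covers one month, that of the last observed date. A stop recorded as March 2022 in a subject last observed in September 2022 has no rule on either reading.

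**Effect of a late-date rule** (31 December, no later than the last observed date):

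| Onset | True stop | Last observed | True duration | Stop set to 1 January | Capped 31 December |
|---|---|---|---|---|---|
| 15 Jun 2021 | 24 Jun 2021 | 1 Mar 2022 | 10 | -164 | 200 |
| 1 Dec 2021 | 30 Jun 2022 | 1 Nov 2022 | 212 | 32 | 336 |
| 10 Feb 2022 | 1 Mar 2022 | 15 Sep 2022 | 20 | -39 | 218 |

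The late-date rule removes impossible values whenever the AE starts on or before the last observed date. It does so by overstating duration.

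**The case against.** The strongest reply is that very little depends on this bullet. The imputation is stated to be for AE duration only. The summaries in SAP 9.3.1 count subjects and events by SOC, PT, severity, relationship, cycle group and route. The event rates there divide by drug exposure, not by AE duration. No duration table is named, and the only named output is the protocol's AE listing, which shows onset and stop dates beside the duration. Year-only stop dates may also be uncommon: the protocol has AEs asked about at each visit, makes the resolution date a reporting item, and provides for data clarification with sites. All of this stands, and it limits the size of the point.

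It is also fair to say that negative durations follow only if someone applies a sentence about start dates to stop dates. That is right, but the other reading leaves no rule, so the text is defective either way.

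The medication rule is weaker evidence than it looks. It serves to classify concomitant use, where a late stop date is the inclusive choice. It supports the view that the AE bullet is a copying slip, but it does not show that 31 December is the right date for a duration.

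A reader might infer that TEAE classification or the incidence tables are affected. The documents do not support that, since stop-date imputation is limited to duration. One neighbouring point is merely unclear. Where the start date is wholly missing, an AE is not counted as a TEAE if its stop date is present and precedes the first dose. The SAP does not say whether a year-only stop counts as present for that purpose.

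**Conclusion.** The point holds as a drafting defect in an operative rule. As written, year-only AE stop dates either become 1 January, which gives a negative duration for 363 of 365 same-year onsets and a shortfall of up to 364 days for earlier-year onsets, or they have no rule at all. Day-only gaps outside the month of last observation have no rule on either reading. No other section of the SAP or protocol supplies one, and the SAP's section on changes from the protocol does not mention it.

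The consequence is small: it reaches AE duration and not the TEAE tables. The number of affected dates is not given, so the total effect on the listing cannot be sized. The figures assume 365-day years, a complete onset date unless stated otherwise and, for the averages, true dates spread evenly. A reader might conclude that the SAP will produce negative durations. The text does not establish that; it establishes that the plan contains no valid rule to prevent them.

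**What to change.** In SAP 8.4.3.1, keep the first stop-date bullet and replace the other two with a rule along these lines: if the stop day is missing, use the last day of that month; if the stop day and month are missing, use 31 December; in both cases no later than the last observed date and never before the AE start date. Flag imputed durations in the AE listing.

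The drawback should be stated in the SAP: this is an upper bound and can greatly overstate short events (a true 10 days becomes 200 in the first example). It is consistent with the first two existing stop-date bullets, which also move to the last observed date. Showing duration as missing for year-only stop dates is an acceptable alternative that avoids the overstatement.

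The cost is one or two SAP lines and a listing flag, with no change to data collection. It is best done before database lock, because the SAP requires departures from the planned analysis to be described and justified in the study report.

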9.1.6. Study Medication Exposure and Compliance

Study medication exposure during MT-1186-A03 will be calculated as specified in section 8.4.1.4. The following information will be summarized and listed for the safety analysis population:

- The number of subjects exposed to study treatment
- The number of subjects exposed to study treatment by oral administration
- The number of subjects exposed to study treatment by PEG/RIG administration
- Duration of exposure of study treatment (days) by Cycle and Total
- Total duration of exposure to study treatment, expressed as person years (sum of exposure to study treatment)
- Total duration of exposure (days) under PEG/RIG administration
- Time to date subjects switched to PEG/RIG administration

Treatment compliance will be determined by performing study treatment accountability of returned study treatment used and unused according to section 8.4.1.4. Treatment compliance will be summarized and listed for the safety analysis population using descriptive statistics. Non-compliance is defined as taking $< 80\%$ or $> 120\%$ of study medication during evaluation periods. The proportions of subjects with non-compliance as defined above will be summarized and listed for the safety analysis population.

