9.3.1. Adverse Events

AEs that occurred on or after the first dose in the MT-1186-A03 will be summarized, which implies AE that occurred during MT-1186-A01 will not be summarized.

The following summaries will be provided:

- A Summary table of the overall incidence (number and percentage) and the number of events will be provided for TEAE, TEAE related to study drug, severe TEAEs, TESAEs, TEAEs leading to study treatment discontinuation and TEAEs leading to death.

The numbers and proportions of subjects will be calculated for the following:

- TEAEs by SOC and PT
- TEAEs by SOC, PT and severity
- Most Common ($\geq 5\%$ of patients) TEAEs by SOC and PT
- TEAEs related to study drug by SOC and PT
- TEAEs related to study drug by SOC, PT and severity
- TESAEs by SOC and PT
- TESAEs related to study drug by SOC and PT
- Severe TEAEs by SOC and PT
- Severe TEAEs related to study drug by SOC and PT
- TEAEs leading to study treatment discontinuation by SOC and PT
- TEAEs by SOC, PT and relationship to study drug
- TESAEs by SOC, PT and relationship to study drug
- TEAEs leading to death by SOC and PT

For these tables, SOC will be sorted by International Agreed Order; then within SOC, PT will be sorted by PT code.

The following summaries will be provided:

- A Summary table of the overall incidence (number and percentage) will be provided for Peripheral Neuropathy Standardized MedDRA query (SMQ) TEAEs

The numbers and proportions of subjects will be calculated for the following:

- TEAEs of Peripheral Neuropathy SMQ by SOC and PT
- Serious TEAEs of Peripheral Neuropathy SMQ by SOC and PT

TEAEs by Oral/PEG subgroup, SOC and PT

The numbers and proportions of subjects with TEAEs and event rate of TEAEs will be calculated by Oral/PEG subgroup, SOC and PT. The event rate of TEAEs will be calculated as the number of TEAEs divided by total exposure to investigational product by Oral/PEG dosing and expressed as 100 person years. Any TEAE occurred after subject switched to PEG will be classified under the PEG subgroup.

The exposure (in days) under Oral in cycle switched to PEG will be calculated as difference: Oral days=PEG switch Date during MT-1186-A01 or MT-1186-A03 - Cycle first date. If Oral days is less than 0 then Oral days will be 0.

The oral days does not exceed actual exposure duration (days) in the cycle. The exposure under PEG will be calculated as difference:

PEG days= actual exposure duration - Oral days.

TEAEs by Cycle

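### In the Oral/PEG event-rate table, events and exposure are split at the switch by different rules, which can bias the rates, mainly the PEG rate

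*SAP*

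**What the plan says.** SAP 8.4.3.1 (Definition of TEAE under Oral dosing and PEG dosing) assigns events by date: "TEAEs after the switched date will be defined as TEAEs under PEG dosing. Otherwise TEAEs will be defined as TEAEs under Oral dosing". SAP 9.3.1 restates this for the rate table: "Any TEAE occurred after subject switched to PEG will be classified under the PEG subgroup". Neither sentence names the switch day, but under the first anything not strictly after that date is Oral.

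Exposure is split in SAP 9.3.1, for the cycle that contains the switch: "Oral days=PEG switch Date during MT-1186-A01 or MT-1186-A03 - Cycle first date". There is a floor ("If Oral days is less than 0 then Oral days will be 0") and a cap ("The oral days does not exceed actual exposure duration (days) in the cycle"). The rest goes to the tube: "PEG days= actual exposure duration - Oral days".

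Actual exposure is defined in SAP 8.4.1.4 in dosing days: 10 planned per cycle, minus days missed, plus additional days. The rate is the number of TEAEs over exposure by route, per 100 person-years. SAP 9.1.6 also reports "Total duration of exposure (days) under PEG/RIG administration", and 9.3.1 gives the only formula for that split.

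**The concern.** A rate needs its numerator and denominator cut at the same point and counted in the same unit. Here they are not.

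- **Boundary.** A subject who switches on the first day of a cycle has 0 Oral days in that cycle, yet an event on that day is an Oral TEAE.
- **Unit.** Calendar days before the switch include off-days and missed doses. Subtracting them from a count of doses takes exposure away from PEG.

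The Oral/PEG table is the only safety table by route that the SAP plans. PEG exposure is likely to be much the smaller of the two, so the PEG rate is where an error would show.

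**Working it through.** The documents give no route-specific rate or exposure total, so there is no figure to reproduce. The check applies the SAP formula as written and compares it with a direct count of doses.

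**Inputs from the documents.** 28-day analysis cycles (SAP 8.6). Ten planned dosing days per cycle (8.4.1.4), taken within a 14-day period and not stated to be consecutive (4.1). Floor, cap and remainder rule (9.3.1).

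**Assumptions.** Each of the 28 possible switch days is equally likely. A switcher has 60 to 120 PEG dosing days after the switch cycle. The documents give neither the number of switchers nor their exposure.

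**Formulas**, for a switch on cycle day d with A doses taken in the cycle:
- SAP: Oral = min(d - 1, A); PEG = A - Oral.
- Direct count: PEG = doses taken on or after day d.

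**One case.** Dosing on days 1-5 and 8-12, d = 8. SAP: Oral = min(7, 10) = 7, PEG = 3. Direct count: 5 and 5.

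**Direction.** With at most one dose a day, a known switch date and dosing that starts no earlier than the analysis cycle, doses before the switch cannot exceed d - 1 or A. SAP Oral days are then never below the true number, so PEG can only be understated.

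**Average over the 28 switch days.** With ten doses, SAP PEG is (10 + 9 + ... + 1)/28 = 55/28 = 1.96. True PEG is the sum of the dosing-day numbers divided by 28. The effect on the PEG rate is (true - SAP)/(later days + SAP), for 120 and 60 later days.

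| Dosing in the switch cycle | True PEG | SAP PEG | Mean (largest) shortfall, days | PEG rate raised by |
|---|---|---|---|---|
| Days 1-10 | 55/28 = 1.96 | 1.96 | 0 (0) | 0 |
| Days 1-5, 8-12 | 65/28 = 2.32 | 1.96 | 0.36 (2) | 0.3% to 0.6% |
| Days 5-14 | 95/28 = 3.39 | 1.96 | 1.43 (4) | 1.2% to 2.3% |
| Days 1-10, first three missed | 49/28 = 1.75 | 28/28 = 1.00 | 0.75 (3) | 0.6% to 1.2% |
| 7 days late, days 8-17 | 125/28 = 4.46 | 1.96 | 2.50 (7) | 2.0% to 4.0% |
| 14 days late, days 15-24 | 195/28 = 6.96 | 1.96 | 5.00 (10) | 4.1% to 8.1% |

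For example, days 5-14 with 60 later days: 63.39/61.96 = 1.023.

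**Same error in every switcher.** A 2-day shortfall raises the PEG rate by 125/123 - 1 = 1.6% with 125 true PEG dosing days each, and by 25/23 - 1 = 8.7% with 25. A 4-day shortfall gives 3.3% and 19%. A 10-day shortfall gives 130/120 - 1 = 8.3% with 130 days and 30/20 - 1 = 50% with 30. With 10% to 40% of 140 subjects switching, the 2-day case lowers the Oral rate by only 0.1% to 0.4%.

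**Switch-day events.** Each one counted as Oral lowers the PEG rate by one event out of all PEG events. If exposure were moved to match the event rule instead, one dosing day per switcher would change the PEG rate by 125/124 - 1 = 0.8% with 125 PEG days and 25/24 - 1 = 4.2% with 25.

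**The case against.** The case against has substance, and several stronger readings that a reader might reach are not supported.

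- **That both rates are simply wrong.** Ten consecutive doses from day 1 give no unit error. Otherwise the error sits in one cycle per switcher. The two faults also pull the PEG rate in opposite directions. That does not cure either of them: one depends on same-day events and the other on gaps, so any cancellation would be chance.
- **That the switch day always counts as PEG exposure.** It does so only while Oral days stay below the doses taken in the cycle. With ten doses, a switch on days 11-28 (18 of 28) leaves PEG at 0 for that cycle.
- **That PEG exposure can never be overstated.** A missing switch day is set to the 15th (8.4.3.1). If the cycle starts on the 15th, doses run on days 1-10 and the true switch is the 20th, the SAP gives Oral 0 and PEG 10 against a true 5 and 5. SAP 8.6 also ignores drift. If the second dosing cycle runs on days 25-34 and the switch is day 29, the SAP gives Oral 0 and PEG 10 against 4 and 6.
- **That PEG exposure is cut by 15% to 42%.** Those are the ratios 1.96/2.32 and 1.96/3.39 for the switch cycle alone. The reported rate pools all cycles.
- **That the SAP contradicts its own rule for the first dose.** The sentence "with a start date equal to the date of first dose of study treatment in the current study will be considered treatment-emergent" applies only to events whose start time is missing. It is a tie-break and shows a preference at another boundary, no more.

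It is also fair to say that the rates are descriptive, that SAP 7.2 plans no hypothesis test, and that the all-subject TEAE tables are untouched. The formula may be a deliberate approximation, because 8.4.1.4 describes missed and additional doses only as counts by CRF visit. That limits the remedy for exposure. It does not explain the different boundaries.

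**Conclusion.** The point holds in a limited form. The SAP cuts events and exposure at different sides of the switch date and subtracts calendar days from dosing days, and no other section reconciles this. The PEG rate can be biased; the Oral rate barely moves. With a known switch date, on-schedule dosing that has gaps, and an assumed 60 to 120 later PEG dosing days per switcher, the exposure error averages about 0.3% to 2.3% of the PEG rate. It grows when PEG exposure is short or dosing runs late, and it can go either way with an imputed switch day or cycle drift. Switch-day events counted as Oral lower the PEG rate by an amount that the documents do not allow one to size. This is worth correcting before database lock, but it does not threaten the study's main safety conclusions.

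**What to change.** 1. In SAP 8.4.3.1 and 9.3.1, use one boundary for events and exposure: PEG TEAEs are those that start on or after the switch date. Where times are recorded, use before or after the first tube dose.
2. In the switch cycle, set Oral days to the number of doses taken before the switch date where dose dates are available. Otherwise use the planned dosing days before the switch, with the assumed dosing pattern stated. Cap this at the actual exposure in the cycle, and set PEG days to the remainder. If the stated assumption is ten consecutive days from day 1, the result equals the current formula; the gain is then only that the assumption is visible.

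The cost is wording in two sections and one derivation. The protocol does not describe this table, so no amendment is needed. The downside is that a same-day event that began before the first tube dose will count as PEG when no time is recorded.

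### The SAP puts subjects who start on PEG/RIG in the PEG subgroup, but without a recorded switch date its event rule counts their TEAEs as Oral and leaves their exposure split undefined

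*SAP*

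**What the plan says.** SAP 8.4.3.1 recognises two kinds of entrant: "The patients start with oral administration or PEG administration". It then gives two rules on route.

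- **Subject level.** A subject belongs to the PEG subgroup "if the subject started with PEG/RIG or switched from oral dosing to receiving study medication through PEG/RIG during MT-1186-A01 or MT-1186-A03"; everyone else is Oral. Starters and switchers are both covered.
- **Event level.** "If the subjects have the date subject switched to PEG/RIG dosing during MT-1186-A01 or MT-1186-A03", TEAEs after that date are under PEG dosing. "Otherwise TEAEs will be defined as TEAEs under Oral dosing". Starters are not mentioned.

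The only repair for an imperfect date is for a missing day: "If a switch date is incomplete and the switch day is missing, then the 15th day will be used". Nothing covers a subject with no switch date at all.

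SAP 9.3.1 plans the TEAE table by route and ties events to a switch again: "Any TEAE occurred after subject switched to PEG will be classified under the PEG subgroup". The event rate is the number of TEAEs "divided by total exposure to investigational product by Oral/PEG dosing and expressed as 100 person years". For the cycle of the switch, exposure is split as "Oral days=PEG switch Date during MT-1186-A01 or MT-1186-A03" minus the first date of the cycle. Negative values are set to 0, the result is capped at the actual exposure in the cycle, and PEG days are what remains. SAP 9.1.6 also asks for total exposure under PEG/RIG and time to switch.

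**The concern.** The two adjacent rules in 8.4.3.1 do not cover the same people. A subject who receives study drug by PEG/RIG from the first MT-1186-A01 dose meets the subgroup rule by name. That subject meets the event rule only if someone has entered a switch date for a switch that never took place. SAP 8.4.3.1 itself describes switching as something that oral starters do.

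The table in SAP 9.3.1 is the only planned comparison of TEAEs by route; the subgroup analyses in SAP 9.4 are by region. Route is a live question in the protocol. The background in Protocol 6.1.1 reports preliminary PEG exposures about 30% above oral in Study MT-1186-J05, judged not clinically significant, and equivalence by nasogastric tube in healthy volunteers in MT-1186-Z-101. A route table whose numerator and denominator follow different rules is a poor check on that.

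**Working it through.** The plan states no figure on this point. The check is to trace one subject through the rules and then show, on assumed counts, how far the result could move.

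**Trace.** Take a fully compliant subject on PEG/RIG from the first MT-1186-A01 dose, with no switch date. SAP 8.4.1.4 plans 10 dosing days in each of 24 cycles, so MT-1186-A03 exposure is 24 × 10 = 240 days, or 240/365.25 = 0.657 person-years.

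1. Subgroup: PEG.
2. TEAEs under PEG dosing: none. All are Oral by the default clause.
3. Exposure split: not defined. There is no cycle of switch and no date to subtract from.

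A programmer has to complete step 3, and three completions are possible:

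- **A.** All 240 days go to Oral, to match the events.
- **B.** The 240 days are lost from both routes.
- **C.** All 240 days go to PEG. A literal SAS step does this: a missing value ranks below 0, so the floor sets Oral days to 0 and the remainder is PEG. SAP section 12 specifies SAS.

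**Illustration.** From the SAP: 140 subjects (4.2) and 240 dosing days each. Assumed: 20 mid-study switchers with 120 Oral and 120 PEG days; 10 TEAEs per 240 Oral days; 15 per 240 PEG days; 5 starters. Rate per 100 person-years = 100 × events / (days/365.25). The SAP counts dosing days only, so the rates look high.

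- Oral days: (140 − 20 − 5) × 240 + 20 × 120 = 30,000. Oral events: 30,000 × 10/240 = 1,250.
- Switchers on PEG: 20 × 120 = 2,400 days and 2,400 × 15/240 = 150 events.
- Starters: 5 × 240 = 1,200 days and 1,200 × 15/240 = 75 events.
- Correct: Oral 100 × 1,250/(30,000/365.25) = 1,522; PEG 100 × 225/(3,600/365.25) = 2,283; ratio 1.50.
- A: Oral 100 × 1,325/(31,200/365.25) = 1,551; PEG 100 × 150/(2,400/365.25) = 2,283; ratio 1.47.
- B: Oral 100 × 1,325/(30,000/365.25) = 1,613; PEG 2,283; ratio 1.42.
- C: Oral 1,613; PEG 100 × 150/(3,600/365.25) = 1,522; ratio 0.94.

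Reported Oral and PEG rates, with the PEG/Oral ratio in brackets, for other numbers of starters (correct: 1,522 and 2,283, ratio 1.50, throughout):

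| Starters | A: exposure to Oral | B: exposure lost | C: exposure to PEG |
|---|---|---|---|
| 0 | 1,522; 2,283 (1.50) | 1,522; 2,283 (1.50) | 1,522; 2,283 (1.50) |
| 1 | 1,528; 2,283 (1.49) | 1,540; 2,283 (1.48) | 1,540; 2,075 (1.35) |
| 5 | 1,551; 2,283 (1.47) | 1,613; 2,283 (1.42) | 1,613; 1,522 (0.94) |
| 10 | 1,580; 2,283 (1.44) | 1,712; 2,283 (1.33) | 1,712; 1,141 (0.67) |

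The damage is modest if events and exposure move together. It is large only when they part, as in C.

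**After the fix.** With the switch dated at the first MT-1186-A01 dose, the date precedes every MT-1186-A03 cycle. The floor then gives Oral days = 0 and PEG days = 240, and all MT-1186-A03 TEAEs fall after it. Subgroup, numerator and denominator agree.

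**The case against.** The strongest reply is that the CRF may already record a PEG start date for these subjects in the switch-date field, for instance the date of first dose. The SAP says that the CRF was consulted in its preparation (section 2), and the CRF is not among the documents. If it does, the rules work apart from possible events on the date itself. This stands as a limit: the absence of a switch date is an inference. It does not remove the conflict in the text, because the SAP nowhere says that starters carry such a date.

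The reply on scope also stands. Only subjects on PEG/RIG from the first MT-1186-A01 dose are affected, and there may be none. The overall, serious, severity, relatedness, discontinuation and death tables do not use route. The study is descriptive, with no hypothesis testing (SAP 7.2), and the TEAE summaries in Protocol 17.3.5.3 have no route breakdown.

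Three stronger readings are tempting, and the documents do not support them:

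- *Exposure also defaults to Oral.* The default clause in 8.4.3.1 covers TEAEs only. SAP 9.3.1 gives exposure no such default, and completion C would send it to PEG.
- *PEG incidence is diluted.* With 30 PEG-subgroup subjects, 5 of them starters, and a TEAE on PEG in all 30 (all assumed), one might report (30 − 5)/30 = 83%. That needs the event-level rule to govern the incidence numerator. SAP 9.3.1 can equally be read as counting subjects by the subject-level subgroup, which gives 30/30. The text does not settle it.
- *Starters have the longest PEG exposure.* SAP 8.4.1.4 counts exposure during MT-1186-A03 only, so a subject who switched during MT-1186-A01 has the same potential 240 days.

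**Conclusion.** The point holds, with narrow scope. For a starter without a switch date, the event rule in SAP 8.4.3.1 contradicts the subgroup rule beside it, and the exposure split in 9.3.1 has no defined value. This is a wrong classification by the stated rule, not merely missing detail.

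The effect is confined to the Oral/PEG TEAE table and the PEG exposure summary. Subjects who switched during MT-1186-A01 are handled correctly, because the rules accept a date from that study and the floor at 0 makes all their MT-1186-A03 exposure PEG.

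The size cannot be stated from the documents. It is nil with no starters. On the assumed inputs with 1 to 10 starters, a true rate ratio of 1.50 is reported as anything from 1.49 down to 0.67, and C gives the lowest values. The conclusion rests on the CRF not supplying a switch date for starters.

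**What to change.** Add to SAP 8.4.3.1 and 9.3.1:

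> For subjects whose first administration in MT-1186-A01 was by PEG/RIG, the PEG switch date is set to the first MT-1186-A01 dose date; all their MT-1186-A03 TEAEs and exposure are under PEG dosing (Oral days = 0).

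The sentence should name the MT-1186-A01 dose. The event rule counts only TEAEs after the date, so a date at the first MT-1186-A03 dose could leave Day 1 events under Oral. Because the assigned date is not a real switch, SAP 9.1.6 should also say whether these subjects are left out of the time-to-switch summary.

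The cost is one sentence in two places and a line of derivation code, with no change to the design. It does require that the route of first administration in MT-1186-A01 is on record, which the existing subgroup rule already presumes.
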